1 INTRODUCTION

This document outlines the statistical methods to be implemented during the analyses of PK/PD data collected within the scope of SIR365-US-101 (A Multicenter, Randomized, Double-Blinded, Placebo-Controlled Study to Assess Safety and Efficacy of SIR1-365 in Patients with Severe COVID-19). The purpose of this plan is to provide specific plans for the statistical analyses of PK/PD data.

2 STUDY DOCUMENTS

The following study documents are used for the preparation of the statistical analysis plan (SAP):

- Protocol, Version 2.4, Apr 8th, 2021
- Annotated electronic case report form (eCRF 2.0 April 26th, 2021)
- Data Management Plan, Version 1.0, Sep 8th, 2020

3 ANALYSIS OBJECTIVES

The objective of Study SIR365-US-101 is to evaluate the safety, tolerability, pharmacokinetics (PK) and pharmacodynamics (PD) of SIR1-365 after oral administrations in patients with severe COVID-19.

To assess the PD effects of SIR1-365, the following biomarker measures will be carried out:

1). Biomarkers Indicative of Inflammation

- Change from Baseline to Day 7 and Day 14 in serum cytokine levels including INF- γ , IL-6, TNF- α , IL-1 β , IL-7, IL-8, IL-9, IL-10, total IL-18, G-CSF, and GM-CSF
- Change from Baseline to Day 7 and Day 14 in serum chemokine levels including CXCL-1, CXCL-9, CXCL-10, MCP-1, MIP-1 α , and MIP-1 β

2). Biomarkers Indicative of CV Endothelial Cell Damage

- Change from Baseline to Day 7 and Day 14 in serum VWF antigen level
- Change from Baseline to Day 7 and Day 14 in serum P-selectin level
- Change from Baseline to Day 7 and Day 14 in serum soluble thrombomodulin level

3). Biomarkers Indicative of Kidney Injury

- Change from Baseline to Day 7 and Day 14 in urine NGAL level
- Change from Baseline to Day 7 and Day 14 in urine KIM-1 level

4). Biomarkers Indicative of Target Engagement

- Change from Baseline to Day 7 and Day 14 in plasma and/or PBMC pRIP1 level
- Change from Baseline to Day 7 and Day 14 in plasma and/or PBMC pMLKL level

4 STUDY DESIGN AND PLAN

This is a multicenter, randomized, double-blinded, placebo-controlled study to evaluate safety and efficacy of SIR1-365 in hospitalized patients with severe COVID-19. The primary objective is to assess the overall safety and tolerability of SIR1-365 administered orally at 100 mg, 3 times per day (TID) for up to 14 days relative to the placebo group. The secondary objectives are to assess the effects of SIR1-365 on clinical efficacy endpoints and the biomarkers indicative of inflammation, target engagement, and kidney injury as well as SIR1-365 PK.

Approximately 60 eligible patients will be randomly assigned at a 1:1 ratio to receive either SIR1-365 at 100 mg TID or matching placebo for up to 14 consecutive days. For ethical and medical reasons, standard-of-care treatments for COVID-19 will be provided to all patients. Thus, the study drugs (either SIR1-365 or matching placebo) will be given as add-on therapy.

Patients could be hospitalized for up to 14 days. Patients will be assessed daily while hospitalized. If the patients are discharged from the hospital before Day 14, no study drugs will be administered. A follow-up visit in person will be performed to obtain safety laboratory tests and blood samples for biomarker analysis as well as clinical outcome data. However, infection control or other restrictions may limit the ability of the patients to return to the clinic. In this case, the follow-up visit may be conducted by phone and only safety data will be obtained. Follow-up visit will be scheduled approximately on Day 28 (± 3) or 14 days after discharge/end of treatment.

5 SAMPLE ANALYSIS

5.1. Measurement of Plasma Drug Levels (PK)

Approximately 60 patients enrolled in the study will have peak and trough blood samples obtained within 30 min before and 2 hours (± 5 min) after the 1st dose on Day 1, respectively. On

Day 7 and Day 14, one blood sample will be collected within 30 min before and 2 hours (± 5 min) after the 2nd dose, respectively.

Samples may be collected at additional time points during the study if warranted and agreed upon between the Investigator and the Sponsor. Instructions for the collection and handling of biological samples will be provided by the Sponsor. The actual date and time (24-hour clock time) of each sample will be recorded.

Drug concentration information that may unblind the study will not be reported to investigative sites or blinded personnel.

5.2. Measurement of Biomarker Levels (PD)

5.2.1. Measurement of Biomarkers Indicative of Inflammation

5.2.1.1. Cytokines

Serum cytokines including INF- γ , IL-6, TNF- α , IL-1 β , IL-7, IL-8, IL-9, IL-10, total IL-18, G-CSF, GM-CSF will be measured at a central laboratory.

5.2.1.2. Chemokines

Serum chemokines including CXCL-1, CXCL-9, CXCL-10, MCP-1, MIP-1 α and MIP-1 β will be measured at a central laboratory.

5.2.2. Measurement of Biomarkers Indicative of Kidney Injury

Urine NGAL and KIM-1 levels will be measured at a central laboratory.

5.2.3. Measurement of Biomarkers Indicative of CV Endothelial Cell Damage

Serum VWF antigen, P-selectin and soluble thrombomodulin levels will be measured at a central laboratory.

5.2.4. Measurement of Biomarkers Indicative of Target Engagement

Levels of pRIP1 and pMLKL in plasma and PBMC will be measured at a central laboratory.

PBMC preparation will be done at the sites with necessary equipment according to the laboratory manual for pRIP1/pMLKL assay.

6 STATISTICAL ANALYSIS

6.1. General Analysis Considerations

The statistical analyses will be reported using summary tables, listings, and figures (TFLs). Unless otherwise noted, all statistical testing will be 2-sided and will be performed at the 0.05 significance level. Tests will be declared statistically significant if the calculated P value is <0.05 .

Continuous variables will be summarized by presenting the number of observations, mean, standard deviation. Other summaries (e.g., 95% confidence interval [CI]) may be used as appropriate. Categorical variables will be summarized by presenting counts and percentages of patients in corresponding categories. Footnotes in the table will specify the percent basis in those cases.

All summary tables will be presented by treatment group. PK/PD data, and any derived data will be presented by patient in data listings.

The analyses described in this plan are considered a priori, in that they have been defined before unblinding.

[figure not shown]
All analyses and tabulations will be performed using R (version 4.0.1 or higher) or SAS (Version 9.4 or higher).

All analyses will be conducted by a designated statistician. The programming code, results, analysis report will be independently reviewed by another statistician.

[figure not shown]
6.2. Analysis Set

All patients who receive study drug without major protocol deviation related to PK/PD analysis and have sufficient PK/PD data to obtain reliable estimates of the key PK/PD variables. Treatment assignment will be based on the treatment actually received.

If a sample yields invalid assay results for all the biomarkers, the data will not be imputed. If a sample has both valid and invalid assay results, the biomarkers with failed assay will be imputed by the overall mean of the same biomarker measured at the same time point within the same treatment group. If the assay passed QC but the result is BLQ, it will be imputed as 0. This process is shown by the flow chart below.

All plasma drug levels below the limit of quantitation (BLQ) values will be imputed as zero (0). If a sample yields invalid assay result, the data will not be imputed. The process is shown by the flow chart below.

For the analysis of both PK and PD biomarker data, if the sample was collected before or on Day 7, the time is labelled as Day 7; if the sample was collected after Day 7, the time is labelled as Day 14.

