## 10.2. Populations for Analyses

For purposes of analysis, the following populations are defined:

Population	Description
Safety set	All patients who are randomized and take at least 1 dose of study drug (SIR1-365 or placebo). Patients will be analyzed according to the treatments received.
Intention-to-Treat (ITT) set	All patients who are randomized to the study
Modified Intention-to-Treat (mITT) set	All patients who take at least one dose of study drug and have at least one follow-up outcome evaluation
Per protocol (PP) set	All patients who take at least one dose of study drug and do not have the important major protocol deviation
PK/ PD set	All patients who receive study drug without major protocol deviation and have sufficient PK/PD data to obtain reliable estimates of the key PK/PD variables

In this study, major protocol deviation categories include the follows:

- ICF not signed
- Violation of key inclusion or exclusion criteria
- Wrong study drug treatment
- Use of prohibited medication(s)
- Major GCP violation such as SAE reporting requirement

In regard to establishing a PP set, the decision as to whether a deviation from the above list of major protocol deviations warrants exclusion of the patient from the analysis set will be determined and documented prior to unblinding.

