## 10.3. Statistical Analyses

A detailed SAP will be developed and finalized before database lock.

A 2-sided alpha-level of 0.05 will be used for construction of confidence intervals. No adjustment for multiple endpoints will be employed. Although the study is not powered for hypothesis testing,

p-values will be generated to aid interpretation in addition to confidence intervals about the estimates.

The safety population will be the primary population for safety analysis. Analyses will be performed on observed data.

For clinical efficacy endpoints, the primary analysis will be in the ITT population. Rules for addressing missing data will be detailed in the statistical analysis plan. Sensitivity analyzes for the clinical efficacy endpoints may be performed in the mITT and/or PP populations.

The mITT population will be primary population for the biomarker analysis with exception of time to 50% reduction of CRP levels for which the ITT population will be primary. Sensitivity analyses incorporating imputation for missing biomarker values may be performed.

In general, baseline for each parameter is the last non-missing value collected prior to the first dose of study medication including pre-dose measurements made on the date of the first dose of study medication.

All data analyses will be conducted using SAS® (SAS Institute, Inc, Cary, North Carolina) software. In general, for descriptive summaries, continuous variables will be summarized using the mean, standard deviation, median, minimum value, and maximum value. Categorical variables will be summarized using frequency counts and percentages. All data will be presented in data listings.

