9 ANALYSIS SETS

The following population will be used for safety analyses:

- Safety set
All patients who are randomized and take at least 1 dose of study drug. Treatment assignment will be based on the treatment actually received.

The following populations will be used for efficacy analyses:

- Intention-to-Treat (ITT) set
All patients who are randomized to study. Treatment assignment will be based on the randomized treatment.
- Modified Intention-to-Treat (mITT) set
All patients who take at least one dose of study drug and have at least one follow-up efficacy or biomarker outcome evaluation. Treatment assignment will be based on the randomized treatment.
- Per Protocol (PP) set
All patients who take at least one dose of study drug and do not have an important major protocol deviation. Treatment assignment will be based on the treatment actually received.

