15 CHANGES TO PROTOCOL-SPECIFIED ANALYSES

No changes to protocol-specified analysis.

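### The PK/PD plan tests its secondary biomarkers only on an as-treated set with exclusions, although the protocol makes mITT primary for biomarkers, and it does not declare the departure

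*SAP*

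**What the plan says.** Protocol 10.3 (Statistical Analyses) states: "The mITT population will be primary population for the biomarker analysis with exception of time to 50% reduction of CRP levels". That single CRP endpoint goes to ITT. Protocol 10.3.3 (Biomarker Analysis) covers the kidney-injury markers and other marker families as well as CRP; drug levels have their own section, 10.3.4.

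The main SAP, section 9, defines mITT as "All patients who take at least one dose of study drug and have at least one follow-up efficacy or biomarker outcome evaluation" and adds for that set: "Treatment assignment will be based on the randomized treatment". Its section 1 passes the cytokines, chemokines, target-engagement, kidney-injury and endothelial markers, together with drug levels, to a separate PK/PD plan.

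That PK/PD plan, section 6.2, has one analysis set: "All patients who receive study drug without major protocol deviation related to PK/PD analysis and have sufficient PK/PD data". Patients in it are grouped by the treatment they actually received. Section 6.4 then compares the change from baseline between groups with two-sample t-tests at Day 7 and Day 14.

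The protocol does define a PK/PD set in its section 10.2: "All patients who receive study drug without major protocol deviation and have sufficient PK/PD data to obtain reliable estimates of the key PK/PD variables". It assigns no analysis to that set and does not say how patients in it are grouped.

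**The concern.** The protocol and the PK/PD plan name different populations for the same endpoints, and the PK/PD plan does not mention the difference. Two features of the plan's set matter. It removes patients for deviations, some of which can occur after randomisation, and for having too little data, without defining either how much is enough or which deviations count as PK/PD-related. It also groups by treatment received rather than by randomised arm.

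If exclusion is related both to outcome and to arm, the remaining patients no longer give an unbiased between-arm contrast. CRP, ferritin and white-cell results would come from mITT (ITT for time to 50% CRP reduction), while cytokines and the other markers would come from a possibly different group of patients in the same trial. Protocol 10.1 says the study should supply treatment-difference estimates for some biomarkers for planning later studies, so the population behind those estimates should be the stated one.

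**Working it through.** The documents give no figure to reproduce here: no power, effect size, SD or dropout rate is stated, and the 30 per group is not derived from a formula. The main check compares the texts.

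| Feature | Protocol 10.3 with main SAP 9 (mITT) | Protocol 10.2 (PK/PD set) | PK/PD plan 6.2 |
|---|---|---|---|
| Dosed | yes | yes | yes |
| Data needed | at least one follow-up evaluation | sufficient PK/PD data, undefined | sufficient PK/PD data, undefined |
| Deviations that exclude | none | any major deviation | major deviations related to PK/PD analysis, not listed |
| Grouping | randomised arm | not stated | treatment received |
| Role for biomarkers | primary | none assigned | the only set |

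**Could another clause authorise the switch?** Protocol 8.4 says that the PK analysis plan supersedes the protocol. That sentence closes a paragraph on plasma concentrations, in a section on PK; biomarkers are in 8.3. Main SAP 14 uses mITT unless otherwise specified, but that wording cannot amend protocol 10.3.

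**How many comparisons rest on this set?** The t-test shell in the PK/PD plan lists 30 marker rows at two time points: 30 × 2 = 60 between-treatment p-values. All come from this one set.

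**How large could the effect be?** The exclusion rates and outcome gaps below are assumptions; the documents give neither.

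If a fraction p of an arm is excluded, and the excluded patients' mean change is d SD worse than that of the retained patients, the retained mean differs from the full-arm mean by p × d.

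- One arm loses 20%, d = 1: 0.20 × 1 = 0.20 SD.
- Other arm loses 10%, d = 1: 0.10 × 1 = 0.10 SD.
- Shift in the contrast: 0.20 − 0.10 = 0.10 SD. The sign depends on which arm loses more.
- Standard error of the contrast at 30 per arm: √(1/30 + 1/30) = √(2/30) ≈ 0.26 SD.
- Ratio: 0.10 / 0.26 ≈ 0.4 standard errors.

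A second illustration excludes k patients from one arm of 30 and none from the other. There is no true effect and the SD is unchanged. The bias is (k/30) × d, the standard error is √(1/(30 − k) + 1/30), and the test is two-sided at 0.05 with a normal approximation:

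| k | d (SD) | Bias (SD) | Type I error |
|---|---|---|---|
| 1 | 0.5 to 1.0 | 0.017 to 0.033 | 5.05% to 5.19% |
| 3 | 0.5 to 1.0 | 0.05 to 0.10 | 5.41% to 6.64% |
| 6 | 0.5 to 1.0 | 0.10 to 0.20 | 6.54% to 11.3% |

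A few exclusions barely matter; several informative exclusions from one arm would.

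**The case against.** The opposing case is substantial, and much of it stands.

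- **The set is not new.** The protocol defines a PK/PD set in almost the same words, and more broadly, since any major deviation excludes. This stands: a reader should not infer that the PK/PD plan invented the set. The departure lies in making it the only set for these markers and in adding as-treated grouping.
- **The exclusion is narrow.** Only deviations related to PK/PD analysis count, so the text does not support the reading that everyone with a major deviation is dropped.
- **Selective loss of bad outcomes is conjecture.** One might argue that worsening patients receive prohibited drugs and are then removed, mostly from the worse arm. Use of prohibited medication is a listed major deviation, but the corticosteroid and immunomodulator entries in protocol 6.7.2 are worded as pre-screening windows, and 6.7.1 permits guideline standard of care. Some on-study restrictions do exist (CYP2C19-metabolised drugs, stopping baricitinib, the corticosteroid limit in 6.7.1), so exclusions after randomisation are possible. Nothing in the documents shows their rate or direction.
- **As-treated grouping rarely bites.** It matters only if a patient receives the wrong drug. That is itself a listed major deviation and would probably lead to exclusion first.
- **mITT is not fully randomised either.** It requires a dose and a follow-up evaluation. A patient with no usable change value contributes nothing to a t-test in either set, so the data requirement changes little. But mITT keeps the randomised arm and does not exclude for deviations.
- **The main SAP is weak evidence.** It delegates these markers, so its section 15 statement, "No changes to protocol-specified analysis", cannot be read as a false declaration about the PK/PD plan. Protocol 10.3 carries the point.
- **Deviations are identified before unblinding** (main SAP 10.3). This limits data-driven choices but does not remove selection on events after randomisation. The protocol's rule for deciding exclusions before unblinding is written only for the PP set.
- **The endpoints are exploratory.** Protocol 10.3.3 promises only summaries for most of these markers. This lowers the severity, but the PK/PD plan itself adds the between-arm tests.

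**Conclusion.** The conflict holds as a matter of text. For the markers delegated to the PK/PD plan, the protocol's primary population is not used, no mITT version is planned, and the change is neither declared nor justified. CRP, ferritin and white-cell markers are not affected.

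The statistical consequence is a possible bias of unknown size and sign. The 0.10 SD shift and the type I error figures rest entirely on assumed exclusion rates and outcome gaps, and they support no claim that the results will favour either arm. At the assumed rates the shift is well inside sampling error. Severity is minor to moderate: these are secondary endpoints in a phase 1b study that is not powered for them, and the primary outcome, treatment-emergent adverse events, is untouched.

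**What to change.** In PK/PD plan 6.2 and 6.4, run the between-arm biomarker tests primarily on the mITT set as defined in the main SAP, by randomised arm. Keep the PK/PD set for the drug-concentration summaries and as a supportive biomarker analysis. For that set, define sufficient data and list which deviations count as PK/PD-related. Decide and document all exclusions before unblinding, as the protocol already requires for the PP set. If the sponsor prefers to keep the PK/PD set as primary, the plan should declare the departure from protocol 10.3 and justify it.

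The cost is revised wording and one extra run of the same programs. The imputation rules in 6.2 are a separate matter and are not settled by this change.

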6.4. Statistical Analysis of Biomarker Data

For each marker, raw signal value, change from baseline, and percentage change from baseline will be analyzed. Summary statistics (for raw signal measurements, change from baseline, and percentage change from baseline) will be reported for each marker at baseline, Day 7, and Day 14 by treatment group.

Line plots of change and percentage change from baseline will be presented for each marker. Each line illustrates the value of a PD marker (Y-axis) changes over time (X-axis) of a single subject. Each marker will be represented by one line plot, in which all the subjects are included, treatment groups will be labelled by different colors. In addition, mean +/- stderr line plots will be generated for the two treatment groups.

For pRIP1 and pMLKL, similar line plots will be presented for pre-dose and post-dose separately. Specifically, Day 1 pre-dose and Day 1 post-dose values will be used, respectively, as the baseline for the calculation of the change from baseline for pre-dose and post-dose plots.

One-sample t-test will be used to evaluate if the change from baseline (Day 7 and Day 14 respectively) is significant (i.e., if the change is different from zero). This will be performed for each treatment group separately. Two-sample t-test will be performed to evaluate if the change is different between the two treatment groups. Test will not be performed on percentage change.

Boxplots will be used to graphically represent the data in the 1-sample and 2-sample tests, the test p-value will be displayed in the boxplots.

Heatmap will be used to visualize the percent change of the all the markers (by marker types) for all the subjects.

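### The PK/PD plan fills a failed biomarker assay with its own arm's mean and, on the natural reading, t-tests the filled data, so standard errors and p-values can be too small

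*SAP*

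**What the plan says.** All of this is in the PK/PD analysis plan.

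- **Partly valid samples (6.2).** "If a sample has both valid and invalid assay results", each failed marker is "imputed by the overall mean of the same biomarker measured at the same time point within the same treatment group".
- **Wholly invalid samples (6.2).** "If a sample yields invalid assay results for all the biomarkers, the data will not be imputed". Invalid plasma drug results are not filled either.
- **Results below the limit of quantitation (6.2).** "If the assay passed QC but the result is BLQ, it will be imputed as 0".
- **Tests (6.4).** Change from baseline at Day 7 and at Day 14 is tested within each arm by a one-sample t-test. Between arms, "Two-sample t-test will be performed to evaluate if the change is different between the two treatment groups".
- **Displays (6.4).** "mean +/- stderr line plots will be generated for the two treatment groups", and "the test p-value will be displayed in the boxplots".
- **Significance (6.1).** "Tests will be declared statistically significant if the calculated P value is" below 0.05, two-sided.

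Neither 6.2 nor 6.4 excludes filled values from the tests, adjusts n or the degrees of freedom, adds variance for the imputation, or plans an analysis without filled values. Section 6.4 does not say outright that filled values are tested. The flow charts that accompany 6.2 are not shown in the available text.

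Protocol 10.3 mentions imputation of missing biomarker values only as an optional sensitivity analysis.

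**The concern.** This is single mean imputation by arm. A filled value sits exactly on its arm's mean, so it adds nothing to the spread of that marker at that visit, yet it counts as a full observation. An ordinary t-test cannot tell it from a measurement. The SDs of raw values shrink, their error bars shrink further, and p-values for change can be too small.

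The results table shell lists 30 marker series, including the target-engagement markers, at two visits. That gives 60 between-arm p-values plus the within-arm ones, each read against 0.05. The sample-size section says the trial's biomarker estimates are meant to help plan later studies, so SDs that are too small would carry forward. The single-patient line plots and heatmaps would also show an arm mean as if it were a patient's result.

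**Working it through.** The plan gives no error-rate or power calculation for these tests, so there is no figure of its own to reproduce.

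**Inputs from the documents.** About 30 patients per arm, 1:1 allocation; two-sided 0.05; t-tests on change at Day 7 and Day 14; 30 marker series.

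**Assumptions.** Failures occur at random, in a share f = 5%, 10% or 20%. Correlation between visits is r = 0.3 to 0.8. SDs are a (baseline) and b (post-baseline).

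**Raw means.** With m measured values out of n after filling, reported SE / true SE = sqrt[(m-1)/(n-1) × m/n]. For m = 27 and n = 30 this is sqrt(26/29 × 27/30) = 0.898. The SD ratio is sqrt(26/29) = 0.95. Error bars are too short by about the fraction f.

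**Change, post-baseline values filled only.**

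(reported SE / true SE)² = [a² + (1-f)b² - 2(1-f)r·a·b] / [a² + b²/(1-f) - 2r·a·b]

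- With a = b this equals 1-f for any r, so the SE ratio is sqrt(1-f): 0.975, 0.949 and 0.894.
- With b = a/2 and f = 20% it is (1.2 - 0.8r)/(1.3125 - r). The SE ratio is then 0.974, 0.992 and 1.022 for r = 0.3, 0.5 and 0.7, so there is almost no effect.
- With b = 2a, r = 0.5 and f = 20% it is 2.6/4, an SE ratio of 0.81, which is worse than the equal-SD case.

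**Change, same f filled at both visits, independent failures.** The reported variance is (1-f)(a² + b²) - 2(1-f)²r·a·b, and the true variance is (a² + b²)/(1-f) - 2r·a·b. Their ratio is (1-f)², so the SE ratio is 1-f for any a, b and r. If the same patients fail at both visits, (1-f)(a² + b² - 2r·a·b) is divided by (a² + b² - 2r·a·b)/(1-f), and the SE ratio is again 1-f.

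**Simulated two-sample type I error under no effect.** Simulation A used 10,000 runs per setting (Monte Carlo error about 0.4 points), 20 or 30 per arm, r = 0.3 to 0.7, and normal or log-normal data. Simulation B used 40,000 runs, 30 per arm and normal data, with the same patients failing at both visits where both are filled.

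| Setting | f | SE ratio (formula) | Type I, A | Type I, B |
|---|---|---|---|---|
| Post-baseline only, a = b | 5% | 0.975 | 4.3-5.8% | not run |
| | 10% | 0.949 | 5.1-6.6% | 6.2% |
| | 20% | 0.894 | 6.9-8.3% | 7.7-7.8% |
| Both visits | 5% | 0.95 | 4.8-6.6% | not run |
| | 10% | 0.90 | 6.7-8.2% | 7.7-7.9% |
| | 20% | 0.80 | 11.0-12.7% | 11.6-12.0% |
| Post-baseline only, b = a/2 | 20% | 0.97-1.02 | 3.4-5.8% (all f) | 4.0% (r = 0.8), 5.7% (r = 0.3) |
| Failed assays left missing | 10%, 20% | 1.00 | 3.4-5.6% (all settings) | 4.9% |

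With no failures, A gives 3.7-5.4% and B gives 5.1%. In B the one-sample tests are inflated to a similar degree. In B, b = 2a with r = 0.5 and 20% failed post-baseline gives 11.5%.

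**Small fixed counts** (40,000 runs, normal data, equal SDs, failures post-baseline). With 1, 2 or 3 failures per arm, type I error is 5.4-5.6%, 6.3% and 6.8-7.0% at 20 per arm, and 5.3%, 5.6-5.8% and 6.2-6.5% at 30 per arm.

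**Across the table of tests.** 30 × 2 = 60 between-arm p-values. With no true effect and no filling, 60 × 0.05 = 3 are expected below 0.05. If 10% were filled at both visits in every series, 60 × 0.067 to 60 × 0.082 = 4.0 to 4.9 are expected.

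**The case against.** The strongest reply is that the failure rate is unknown and may be low. The rule acts only on partly failed samples. At about 5% failures the error rate is close to nominal, and where baseline is much more variable than the later visit it can be slightly conservative. At such rates the absence of any multiplicity adjustment does more harm. These are secondary biomarkers in a phase 1b study that is not powered for testing. This all stands and limits the size of the problem. It does not make the rule sound, because the plan commits to it whatever the failure rate turns out to be.

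The flow charts might restrict where filled values are used. That is possible, and it is why the reading is called natural and not certain.

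Protocol 10.3 is permissive and does not forbid imputation in the main analysis. Protocol 8.4 lets the PK analysis plan override the protocol, although that clause follows a sentence about plasma concentrations. So this is at most an unexplained departure, not a contradiction, and the statistical point does not depend on it.

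Under random failure the fill does not bias arm means, and dropping pairs discards an observed baseline. With equal SDs and post-baseline failures, the complete-pair variance minus the filled variance is proportional to f(1-2r)/(1-f), so the filled estimator is the more precise one when r is below 0.5. This is true but does not rescue the t-test, whose standard error is still wrong.

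The figure of 4 to 5 p-values assumes the same 10% rate in all 30 series at both visits. It is an illustration, not a forecast.

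**Conclusion.** The concern holds and should be fixed. As written, 6.2 gives main-analysis status to a fill that overstates n, and nothing in 6.4 corrects for it. Error bars for raw means are too short by about the share of values filled. For change, the reported SE is a factor of sqrt(1-f) too small when only post-baseline values fail and the SDs are equal, and a factor of 1-f too small when the same share fails at both visits. The effect is zero without partly failed samples, small at about 5%, and material from about 10% in most settings. The exception is post-baseline-only failure with a much larger baseline SD.

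These sizes rest on random failure and on assumed failure rates, correlations and SDs. They also rest on reading 6.4 as applying to the filled data. The primary safety endpoint is untouched.

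A smaller, descriptive point: a baseline below the limit of quantitation that is set to 0 leaves percentage change undefined. Percentage change is summarised and plotted but not tested.

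**What to change.** In PK/PD plan 6.2, leave failed biomarker assays missing in all tests, summaries and plots. This extends the rule that 6.2 already applies to wholly invalid samples and invalid drug levels. Report measured and failed counts per marker, visit and arm.

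If a filled analysis is wanted, label it a sensitivity analysis, as Protocol 10.3 allows, and use a method that carries the imputation uncertainty. Protocol 10.3.3 already names multiple imputation as an optional supportive analysis for one inflammatory marker, conditional on more than 10% missing in either arm.

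Also state that percentage change is not calculated when the baseline was below the limit of quantitation and set to 0.

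The cost is a wording change and simpler programming. Affected markers will show a smaller n and wider error bars, and some precision is lost where the correlation between visits is low.
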